2.4. PROCEDURES

2.4.1. Training Protocol

The intervention was conducted with two groups following the same supervised combined training protocol, differing only in weekly frequency. The G2x group performed sessions on Tuesdays and Thursdays, while the G3x group participated in sessions on Tuesdays, Thursdays, and Fridays. The training program was carried out at the UFSC rehabilitation center and the strength training room, under the supervision of Physical Education professionals and students.

Initially, the participants underwent two weeks of familiarization aimed at introducing them to the Borg scale (6-20) and providing guidance on the correct execution of strength exercises. This process also sought to ensure proper adaptation to the protocol. The program was structured into three mesocycles, each lasting four weeks, with the goal of progressively increasing training intensity from one mesocycle to the next.

During strength training, participants performed four exercises: bench press, leg press, seated row, and hip abduction machine. Additionally, at the beginning of each mesocycle, load assessments were conducted, in which participants performed the first set at the lower limit of the repetition zone and in the second set, they were instructed to perform the maximum number of repetitions, both with the same load used during the previous mesocycle. As a safety precaution, the number of repetitions was limited to a maximum of 20. Based on the number of repetitions exceeding the lower repetition limit (RE), the load was adjusted to the mesocycle as follows⁽¹³⁾.

Upper limb exercises: Final weight (Kg) = weight used in the test (Kg) + RE/2

Lower limb exercises: Final weight (Kg) = weight used in the test (Kg) + RE

The aerobic training consisted of interval and pyramid workouts performed on treadmills. Intensity was prescribed using the Borg rating of perceived exertion scale (6-20), and higher intensities were achieved through variations in speed or incline. For those

training three times per week, two sessions were focused on speed variation, and one on incline variation. Participants trained twice per week, alternating between sessions of speed variation and incline variation.

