2. METHODS

2.1. EXPERIMENTAL APPROACH TO THE PROBLEM

This study was a pragmatic clinical trial with two intervention groups. Initially, an anamnesis was conducted to collect sociodemographic data and information about the participants health, as well as to investigate their engagement in other physical activities. Subsequently, anthropometric, functional, hemodynamic, and biochemical assessments were performed for two weeks. After these baseline assessments, participants were divided into two groups: one group performed combined training twice a week (G2x), and the other group three times a week (G3x). Both groups followed the same training program, which lasted 12 weeks, with the total exercise volume being higher in the group that trained three times per week due to the increased session frequency. All the assessments performed at baseline were repeated after 12 weeks.

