2.3. SUBJECTS

The participants in this study were individuals enrolled in the Cardiopulmonary Prevention and Rehabilitation Program (PROCOR) which is a community program for individuals with cardiometabolic risk factors offered by the Federal University of Santa Catarina (UFSC). This program provides specialized support for the safe practice of physical exercises and the promotion of cardiovascular health. Due to the structure of the program and the prior enrollment of participants, it was not possible to randomize the groups.

The inclusion criteria were being enrolled in the PROCOR program, having medical clearance to perform physical exercises, presenting one or more cardiometabolic risk factors, and having no physical limitations that could impair the execution of the proposed exercises.

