2.5.2. Balance/Agility

Agility/dynamic balance was measured using the Timed Up and Go (TUG) test⁽¹⁵⁾. The test result was the shortest time to stand up from a seated position, walk 3.00 meters, turn around, and return to the seated position. The TUG was performed at two walking speeds (maximum and usual), with two attempts for each, and the shortest time of each speed was recorded.

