2.5.4. Cardiorespiratory Fitness

Aerobic capacity was evaluated using two tests: the 6-minute walk test (6MWT), which participants completed one attempt, and the result was the total distance covered in that time⁽¹⁴⁾; and the 1000-meter test (1000m), that was developed due to the presence of a ceiling effect observed in the 6MWT in many participants in previous PROCOR training semesters, in which participants also made one attempt, and the score was the total time in seconds to complete the distance, allowing walking and/or running.

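### Section 2.4.1 says only training frequency separates the groups, but the scheduled aerobic mix differs too: 6 of 36 G3x sessions (17%) are moved from incline to speed work

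*Combined protocol and SAP*

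**What the plan says.** Section 2.4.1 (Training Protocol) opens by presenting the groups as "following the same supervised combined training protocol, differing only in weekly frequency". Section 2.1 (Experimental Approach to the Problem) makes a similar statement: "Both groups followed the same training program, which lasted 12 weeks". It adds that total volume is higher in G3x and puts this down to the extra sessions. It does not mention the type of aerobic work.

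The end of section 2.4.1 gives the treadmill content. For those "training three times per week, two sessions were focused on speed variation, and one on incline variation". The next sentence reads: "Participants trained twice per week, alternating between sessions of speed variation and incline variation". That sentence does not name a group, but G2x is the only group that trains twice a week.

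The same section says aerobic intensity was set on the Borg 6-20 scale, with higher intensities reached by changing speed or incline. Section 2.3 (Subjects) states that "it was not possible to randomize the groups".

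**The concern.** The hypothesis in the Introduction is about three weekly sessions against two. To test it cleanly, the third session should add more of the same content. Under the schedule as written, the G3x group trains more often and also spends a larger share of its treadmill sessions on speed.

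This bears on the primary outcome. Sections 2.5.1 to 2.5.4 list seven functional-capacity measures: sit-to-stand, arm curl, TUG at usual speed, TUG at maximum speed, sit-and-reach, 6MWT and 1000 m. Four of them (both TUG versions, 6MWT and 1000 m) are scored on walking or running time or distance, and none of these is described with an incline. The 1000 m test is the most plausible place for an effect of the mix, since "the score was the total time in seconds to complete the distance, allowing walking and/or running". If G3x does better there, the plan as worded would credit the number of sessions, while the altered mix is an alternative explanation that the design cannot separate out.

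**Working it through.** The plan states no session totals, so there is no figure to reproduce. The check is a count from the schedule.

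**Inputs**
- Duration: three mesocycles of four weeks, 3 × 4 = 12 weeks (section 2.4.1; section 2.1 also gives 12 weeks).
- G3x: 2 speed + 1 incline per week (section 2.4.1).
- G2x: two sessions per week, alternating speed and incline (section 2.4.1, reading the twice-weekly sentence as G2x).

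**Scheduled sessions = sessions per week of each type × 12**

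| | Speed | Incline | Total | Speed share |
|---|---|---|---|---|
| G3x as scheduled | 2 × 12 = 24 | 1 × 12 = 12 | 36 | 24/36 = 67% |
| G2x as scheduled | 12 | 12 | 24 | 12/24 = 50% |
| Ratio G3x:G2x | 2.0 | 1.0 | 1.5 | |
| G3x if only frequency differed (G2x mix kept) | 36 × 0.5 = 18 | 36 × 0.5 = 18 | 36 | 50% |
| Ratio to G2x in that case | 1.5 | 1.5 | 1.5 | |

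**Part due to the mix.** Speed: 24 − 18 = 6 more. Incline: 12 − 18 = 6 fewer. The shift is 6/36 = 17% of G3x sessions. The doubling of speed sessions splits into a frequency part, 18/12 = 1.5, and a mix part, 24/18 = 1.33; 1.5 × 1.33 = 2.0.

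**Sensitivity**
- If G2x alternated by whole week instead of by session, 12 weeks still give 12 + 12.
- If the two familiarization weeks change the count to 10 or 14 weeks, G3x has 20 + 10 or 28 + 14 and G2x has 10 + 10 or 14 + 14. The ratios stay at 2.0, 1.0 and 1.5.

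The strength component shows no such difference. The four exercises and the load-adjustment rule are given once, for both groups.

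**The case against.** The strongest reply is that nothing is hidden. The aerobic mix of each group is set out in the same section as the disputed phrase, and section 2.1 acknowledges the higher volume in G3x. A careful reader can work out what was delivered. That is true, and it keeps the point small. But the summary description is still wrong, and section 2.1 explains the volume difference by frequency alone, which would lead a reader to expect both session types to rise in proportion.

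A second reply is that speed and incline are two routes to one prescription. Intensity was set by Borg rating, so the six shifted sessions change how the target exertion was reached and not the exertion asked for. This stands as a reason to expect a small effect. It does not make the two session types interchangeable for a test of walking or running pace.

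Third, the link to outcomes is thin for most measures. The TUG covers 3 m, one version is done at usual pace, and section 2.5.4 reports a ceiling effect on the 6MWT in many earlier participants. This also stands, which is why the 1000 m test is singled out. No effect of the mix is argued for sit-to-stand, arm curl, sit-and-reach or the secondary outcomes.

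Finally, with three sessions and two types no single week can be balanced. That is correct, but balance over two weeks is possible.

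**Conclusion.** The description is wrong as written, and the severity is minor. The groups differ in frequency (36 sessions against 24) and in aerobic mix (67% speed against 50%). The part not explained by frequency is 6 of 36 G3x sessions, or 17%. Confidence is high for these counts. They rest on taking the twice-weekly sentence to describe G2x and on the schedule having been followed. There is no comparable confidence about any effect on outcomes.

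A reader might infer three stronger things that the documents do not support:
- **That the whole doubling of speed sessions is confounding.** Three sessions a week at the G2x mix would already give 1.5 times the speed work. Only the step from 18 to 24 comes from the mix.
- **That a G3x advantage would be produced by the speed work.** Nothing in the documents shows or sizes such an effect, and both session types served the same exertion-based prescription. Allocation was not randomized, which is a larger obstacle to attributing any difference to frequency.
- **That the Thursday-Friday pairing in G3x is a further fault.** The training days are stated openly, and adding a day to a Tuesday/Thursday timetable necessarily changes the spacing.

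The intention-to-treat comparison of the two schedules as assigned is not affected. What changes is the label that can be put on the difference.

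**What to change.** 1. In section 2.4.1, replace the claim that frequency is the sole difference with the contrast as run: G3x, 36 sessions (24 speed, 12 incline); G2x, 24 sessions (12 speed, 12 incline). Make the matching change in section 2.1, where the program is called the same for both groups. Word the conclusion as a comparison of these two schedules, not as an effect of frequency alone. The cost is two edited sentences and some care in the conclusion.

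2. For any training block still to run, alternate session types in G3x too: speed-incline-speed one week, incline-speed-incline the next. Over 12 weeks, six weeks of each pattern give 6 × 2 + 6 × 1 = 18 speed and 6 × 1 + 6 × 2 = 18 incline, the same 1:1 mix as G2x. This needs no added session, staff or equipment, and the training days stay as they are. The small cost is a mix that varies from week to week.

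The methods are written in the past tense. If training is complete, only the first change applies.

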2.5. PRIMARY OUTCOME (FUNCTIONAL CAPACITY)

2.5.1. Strength

Lower limb strength was measured using the 30-second sit-to-stand test. The test result used was the number of repetitions performed in this time, in one attempt⁽¹⁴⁾. Upper limb strength was assessed using the 30-second arm curl test, with a 2.0 kg dumbbell for women and a 4.0 kg dumbbell for men. The test result was the total number of curls completed in a single attempt with the dominant arm⁽¹⁴⁾.

2.5.2. Balance/Agility

Agility/dynamic balance was measured using the Timed Up and Go (TUG) test⁽¹⁵⁾. The test result was the shortest time to stand up from a seated position, walk 3.00 meters, turn around, and return to the seated position. The TUG was performed at two walking speeds (maximum and usual), with two attempts for each, and the shortest time of each speed was recorded.

2.5.3. Flexibility

Flexibility was assessed using the sit-and-reach test, in which participants sat on a mat with their legs fully extended and their feet placed against a box used for the test, reaching forward⁽¹⁶⁾. The total distance reached represented the final score, with two reach attempts recorded.

2.5.4. Cardiorespiratory Fitness

Aerobic capacity was evaluated using two tests: the 6-minute walk test (6MWT), which participants completed one attempt, and the result was the total distance covered in that time⁽¹⁴⁾; and the 1000-meter test (1000m), that was developed due to the presence of a ceiling effect observed in the 6MWT in many participants in previous PROCOR training semesters, in which participants also made one attempt, and the score was the total time in seconds to complete the distance, allowing walking and/or running.

2.6. SECONDARY OUTCOMES

2.6.1. Hemodynamic profile

Three blood pressure measurements were obtained using a portable automatic monitor (OMRON, model HEM-7200, Brazil). Each participant remained seated and in silence for 10 minutes, and then three measurements of blood pressure and heart rate were taken, with a one-minute interval between each. The same procedure was repeated on a second day, resulting in a total of six systolic blood pressure (SBP) and diastolic blood pressure (DBP) measurements (in mmHg) and six heart rate measurements. The final values were determined by calculating the arithmetic mean of the measurements from both days, resulting in the final average. Additionally, mean arterial pressure (MAP) was calculated using the standard equation: $MAP = (SBP + 2 \times DBP) / 3^{(2)}$.

2.6.2. Biochemical Profile

Participants were instructed to fast for 12 hours and retain their usual medication intake. Blood samples were collected through venipuncture using serum separator tubes without anticoagulant. The analyzed biochemical parameters included the lipid profile (total cholesterol, low-density lipoprotein (LDL), high-density lipoprotein (HDL), and triglycerides) and fasting glucose, all expressed in mg/dL. The analyses were performed at the Clinical Biochemistry Laboratory of UFSC. Triglycerides, total cholesterol, and HDL were measured using an enzymatic colorimetric method, while LDL was calculated using Friedewald's formula: $LDL-c = CT - (HDL-c + TG/5)$, where $TG/5$ represents the cholesterol associated with VLDL. All analyses were conducted using the Mindray BS-120 biochemical automation equipment, following the manufacturer's instructions. Renal function was assessed by measuring creatinine levels using a modified Jaffé method.

2.7. STATISTICAL ANALYSES

The data were analyzed using JASP (Version 0.19.3) [computer software]. The characterization variables had their normality and homogeneity tested using the Shapiro-Wilk and Levene tests, respectively. Variables classified as normal are presented as the mean and standard deviation. Categorical variables for characterizing the sample are presented as absolute frequency (sample n) and relative frequency (%). For comparing baseline characteristics between groups, the independent t -test was used for continuous

data and Fisher's exact test for categorical data. To compare adherence between groups, the Wilcoxon rank sum test was used, and data are presented as median and interquartile range (P25-P75).

For the comparison of the group (G2x and G3x) and time (pre-intervention and post-intervention), a 2-way analysis of covariance (ANCOVA) for repeated measures was performed, with the baseline values used as covariates. Outcomes were analyzed by intention to treat (ITT), which included all patients, once randomized, and missing data were imputed with simple imputation, replacing missing values with the last observed value. The significance adopted was 0.05.

REFERENCES

3. Penninx BWJH, Nicklas BJ, Newman AB, Harris TB, Goodpaster BH, Satterfield S, et al. Metabolic Syndrome and Physical Decline in Older Persons: Results from the Health, Aging and Body Composition Study. *J Gerontol A Biol Sci Med Sci*. 2009 Jan 1;64A(1):96–102.

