**EFFECT OF DIFFERENT WEEKLY COMBINED TRAINING FREQUENCIES
ON FUNCTIONAL CAPACITY, HEMODYNAMIC AND ANTHROPOMETRIC
ASPECTS OF ELDERLY PEOPLE WITH CARDIOMETABOLIC RISK
FACTORS**

March 03, 2024

Abstract

Objective: The objective of this study was to compare the effects of two different weekly frequencies of a 12-week combined training period on functional capacity, hemodynamic, and biochemical profile in older people with cardiometabolic risk factors. **Methods:** This is a pragmatic clinical trial. Functional, hemodynamic, and biochemical outcomes were assessed at baseline and after 12 weeks. Participants were divided into two groups: G2x (trained twice a week), and G3x (trained three times a week). Both groups performed the same training program, which consisted of strength and aerobic training with progressive intensity. Data analysis was performed using intention to treat (ITT), employing a 2-way analysis of covariance (ANCOVA) for repeated measures, with the baseline values used as covariates. The significance adopted was 0.05.

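### Baseline is both the pre level of the outcome and the covariate, so the meaning of every term in the model depends on choices the plan does not state

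*Combined protocol and SAP*

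**What the plan says.** Section 2.7 sets out one between-group analysis for all outcomes, including the primary functional measures of section 2.5. The factors are introduced as "For the comparison of the group (G2x and G3x) and time (pre-intervention and post-intervention", and the model as "a 2-way analysis of covariance (ANCOVA) for repeated measures was performed, with the baseline values used as covariates". The abstract repeats it: "employing a 2-way analysis of covariance (ANCOVA) for repeated measures, with the baseline values used as covariates".

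There is only one visit after baseline: "Functional, hemodynamic, and biochemical outcomes were assessed at baseline and after 12 weeks". On allocation, section 2.3 states that "it was not possible to randomize the groups". The test level is given as "The significance adopted was 0.05", without saying whether it is one- or two-sided.

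The section names the software, but does not say:

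- which term (group, time or group-by-time) carries the conclusion;
- whether the covariate is centred;
- whether its slope may differ between the two times.

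**The concern.** With two time levels, the first of which is baseline, adding baseline as a covariate makes half of the model a regression of baseline on itself. The terms in the output then no longer mean what a reader would take them to mean.

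The hypothesis in the introduction is that three sessions a week do better than two. Depending on which line of the output is used and how the model was set up, this one written analysis gives the adjusted 12-week difference, half of it, or a difference in change with no baseline adjustment. The time effect, which readers tend to take as evidence that training worked, may refer to a participant whose baseline value is zero.

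**Working it through.** The documents give no sample size, SD or effect size, so there is no stated figure to reproduce. The check is algebra, followed by simulation under assumed values.

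**Inputs from the documents.** Two time levels, two groups and baseline as covariate (section 2.7); visits at baseline and week 12 (abstract, section 2.1); no randomisation (section 2.3); level 0.05 (section 2.7), taken as two-sided. I read the baseline values as those of the same outcome, which is natural but not spelled out.

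**Notation.** B is the baseline value, Y the week-12 value and G the group. The 12-week ANCOVA is Y = a + τG + βB + e, and τ is the adjusted difference.

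**Step 1: group main effect.** This regresses the mean of the two time levels on G and B:

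(B + Y)/2 = a/2 + (τ/2)G + ((1 + β)/2)B + e/2.

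The coefficient is τ/2 and the residual is e/2, so estimate and standard error are both halved, and t and p do not change.

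**Step 2: group-by-time, with a covariate-by-time term.** Y − B = a + τG + (β − 1)B + e. The coefficient is τ with the same residual, which is the 12-week ANCOVA again.

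**Step 3: group-by-time, with one common baseline slope.** The covariate is the same at both times, so it cancels from the difference and Y − B is regressed on G alone. The estimate becomes τ + (β − 1)Δ, where Δ is the baseline difference between groups.

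**Numerical check of steps 1 to 3.** Assumed: 30 per group, SD 3, slope 0.7. Two simulated data sets:

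| Baseline shift built in | 12-week ANCOVA | Group main effect | Group-by-time, covariate-by-time fitted | Group-by-time, common slope |
|---|---|---|---|---|
| 0 | 1.6746 (F 12.88) | 0.8373 (F 12.88) | 1.6746 (F 12.88) | 1.6375 |
| 1.5 | 0.5072 (F 0.75) | 0.2536 (F 0.75) | 0.5072 (F 0.75) | 0.1356 |

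For step 3 with Δ = 1.5, the formula gives 1.5 − 0.3 × 1.5 = 1.05 for a true effect of 1.5, and −0.45 for a true effect of 0. Over 3,000 simulated trials the averages were 1.05 and −0.46. With a true adjusted effect of 0, the unadjusted change test rejected in 11% to 12% of trials, against about 5% for ANCOVA.

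**Step 4: time effect with no true change.** Assumed: mean 14, SD 4, correlation 0.8.

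*Covariate not centred.* The test is of the expected change at B = 0, which is 14 × (1 − 0.8) = 2.8 even though the true mean change is 0. The residual SD is 4 × √(1 − 0.64) = 2.4. With N participants in all, the standard error is about 2.4 × √(1/N + 14²/((N − 2) × 4²)).

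| Per group | SE | 2.8/SE | Rejection rate, two simulations |
|---|---|---|---|
| 20 | 1.41 | 1.98 | 48%, 48% |
| 30 | 1.15 | 2.44 | 66%, 64% |
| 40 | 0.99 | 2.83 | 79%, 78% |

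*Covariate centred at the grand mean.* The estimate is the raw mean change, so it is right. The error term leaves out the part of the change variance explained by baseline: 5.76 is used where 5.76 + 0.2² × 16 = 6.40 applies. The effective critical value is 1.96 × √(5.76/6.40) = 1.86, a two-sided rate of about 6%, as simulated.

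Under the other assumed values (mean 14, SD 3, slope 0.7, 30 per group), the rates were 86% uncentred and 6.8% centred.

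**The case against.** The strongest reply is that the test of the stated hypothesis comes through intact. In a group-by-time design the interaction is at least as natural an answer as the group main effect. When the covariate-by-time term is fitted, it is exactly the 12-week ANCOVA. Even the halved main effect has the right t and p, so type I error and power are those of ANCOVA. This stands. A reader might infer that the trial's group effect will be published at half its size, or that the between-group test is invalid. The documents support neither, because they do not say which term is reported.

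The second reply concerns the time effect. The high false-positive rates need an uncentred covariate and assumed values for mean, SD, correlation and group size, and the time effect is not the stated hypothesis. This also stands. The honest statement is a range from near nominal to severe.

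Third, baseline residuals of zero might suggest that follow-up comparisons using a pooled error term would be anti-conservative. Section 2.7 specifies no such comparisons. With two time levels the three main tests reduce to regressions on a sum or a difference, which zero variance at baseline does not spoil. No error rate should be attached to this.

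These replies limit the harm but do not repair the plan. Whether the interaction is adjusted for baseline turns on a term that section 2.7 does not mention, and in non-randomised groups that can change the answer.

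**Conclusion.** The concern holds as a mis-specified model whose consequences are partly conditional.

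- **Certain, if the covariate is the same outcome's baseline:** the group main effect is exactly half the adjusted 12-week difference, with unchanged t and p.
- **Conditional on the covariate-by-time term:** the interaction is either the 12-week ANCOVA or the unadjusted difference in change. With an assumed slope of 0.7 and a baseline imbalance of 1.5, these are 1.50 and 1.05 for the same true effect.
- **Conditional on centring:** with no true change, the time effect is falsely significant in about 6% of trials (centred) or about 48% to 79% (uncentred), assuming mean 14, SD 4, correlation 0.8 and 20 to 40 per group.

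The documents do not support saying that the reported effect will be halved, or that the time effect will be spurious. They do show that the only between-group analysis does not define a single estimate, and this affects the primary outcomes.

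**What to change.** Replace the model sentence in section 2.7, and its counterpart in the abstract, with:

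> For each outcome, the 12-week value is analysed by ANCOVA with group as factor and the baseline value of that outcome as covariate; the adjusted G3x-G2x difference with 95% CI is the estimate.

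Report within-group change separately, as the paired mean change with 95% CI, labelled descriptive because there is no untrained control. Do not report the group and time main effects of the present model.

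A pre/post model without the baseline covariate, with group-by-time as the named contrast, is also coherent. In non-randomised groups it can give a different answer from ANCOVA, so the plan must commit to one. ANCOVA keeps the baseline adjustment that section 2.7 already intends. Neither choice removes confounding by other differences between the groups.

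The cost is one sentence in each place and a simpler model. No data are added and no power is lost, since the t statistic equals that of the present group main effect. The document is written in the past tense; if the analysis has already been run, it must be rerun on the same data.

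### With outcomes measured only twice, the missing-data rule carries baseline forward and scores every missing 12-week result as zero change, which can bias the group difference in either direction

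*Combined protocol and SAP*

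**What the plan says.** The combined protocol and SAP has two outcome time points. The Abstract says "Functional, hemodynamic, and biochemical outcomes were assessed at baseline and after 12 weeks", and section 2.1 says "All the assessments performed at baseline were repeated after 12 weeks". Section 2.7 has the same structure: "For the comparison of the group (G2x and G3x) and time (pre-intervention and post-intervention") are the factors, and the model is "a 2-way analysis of covariance (ANCOVA) for repeated measures was performed, with the baseline values used as covariates".

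The only measurements in between are in section 2.4.1: "at the beginning of each mesocycle, load assessments were conducted". These tests set the training weight for the next block and are not outcomes.

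For missing data, section 2.7 says "missing data were imputed with simple imputation, replacing missing values with the last observed value". It applies this within an intention-to-treat analysis of all participants. The documents state no missingness assumption, expected dropout, alternative method or sensitivity analysis.

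**The concern.** With one outcome measurement before the 12-week visit, the last observed value can only be the baseline value. The rule therefore asserts that anyone without a 12-week result neither improved nor worsened, on every primary functional test and every secondary outcome.

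Both groups train, so both may be expected to improve. Entering zeros for the missing pulls each group's mean change towards zero in proportion to its own dropout. If dropout differs between groups, part of that difference is read as an effect of weekly frequency. Equal dropout should not be taken for granted here: the groups differ in how often participants must attend, section 2.3 says that "it was not possible to randomize the groups", and section 2.7 itself plans to compare adherence between groups.

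**Working it through.** **Inputs from the documents.** Two outcome time points (Abstract, 2.1, 2.7); last-value imputation (2.7); baseline as covariate (2.7); significance level 0.05 (2.7). The documents give no sample size, dropout rate, SD or expected change, so there is no plan figure to reproduce.

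**Inputs assumed.** 30 per group; pre-post correlation 0.8; equal baseline means; dropout independent of outcome, so that dropouts have the same mean gain as completers. Changes are in SD units, with positive meaning improvement.

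**Step 1: expected difference.** Let d2 and d3 be the dropout shares in G2x and G3x, and c2 and c3 the true mean changes. Each missing result counts as zero change, so the observed mean change in a group is (1-d) × c, and

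- expected difference (G3x minus G2x) = (1-d3) × c3 - (1-d2) × c2
- bias = -(d3 × c3 - d2 × c2)

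If dropouts do not share the completers' gain, the c in the bias line is the dropouts' own true mean change.

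**Step 2: equal dropout.** With d2 = d3 = d, the difference becomes (1-d) × (c3 - c2). For gains of 0.5 and 0.8 and 20% dropout, 0.8 × 0.30 = 0.24 instead of 0.30. With no true difference, the result is zero.

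**Step 3: unequal dropout, no true difference (gain 0.5 in both).** The rejection rates come from simulated ANCOVAs of the 12-week value on group and baseline. With two time points, modelling the change or the 12-week value gives the same group coefficient once baseline is a covariate.

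| Dropout G2x / G3x | Arithmetic | False difference | Type I error |
|---|---|---|---|
| 5% / 10% | 0.90 × 0.5 - 0.95 × 0.5 | -0.025 | about 5.5% |
| 10% / 20% | 0.80 × 0.5 - 0.90 × 0.5 | -0.05 | about 6% |
| 10% / 30% | 0.70 × 0.5 - 0.90 × 0.5 | -0.10 | about 10% |
| 10% / 40% | 0.60 × 0.5 - 0.90 × 0.5 | -0.15 | about 18% |

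ANCOVA on observed data stayed near 5%. Swapping the dropout rates reverses the sign and gives a false advantage for G3x, the hypothesised direction.

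**Step 4: unequal dropout, true difference 0.30 (gains 0.5 and 0.8).**

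- 30% in G2x, 10% in G3x: 0.90 × 0.8 - 0.70 × 0.5 = 0.72 - 0.35 = 0.37, inflated.
- 10% in G2x, 30% in G3x: 0.70 × 0.8 - 0.90 × 0.5 = 0.56 - 0.45 = 0.11, shrunk. The rejection rate is about 10%, against about 38% with observed data.

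**Step 5: when there is no bias.** The bias is zero with no missing data, if dropouts truly stay at baseline, or if d3 × c3 = d2 × c2. An example of the last is gains of 0.3 and 0.5 with dropout of 25% and 15%: 0.25 × 0.3 = 0.15 × 0.5 = 0.075.

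**The case against.** The strongest reply is that the figures assume dropouts gain as much as completers. In a training study, someone who stops early may keep little of the gain. A change near zero would then be closer to the intention-to-treat truth, and the bias would be smaller. This stands as a limit on the size. It does not rescue the rule, because the plan offers no such argument and the rule imposes exactly zero on everyone, whatever the reason for the missing result.

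It is also fair that small dropout gaps do little harm: at 5% against 10%, the type I error barely moves. The larger figures need gaps of 20 points or more, and the documents do not say whether such gaps occur.

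A reader might go further than the documents allow in three ways:

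- **That the result is certainly biased, or biased in a known direction.** The bias is conditional and its direction depends on unstated dropout and change.
- **That treating imputed values as observed makes the standard error falsely small.** The calculation does not show this. At equal 20% dropout and a common gain of 0.5 SD, the mean standard error was 0.150 against an actual sampling SD of 0.151, with type I error about 5%. The standard error is below that of the observed-data analysis (by about 14% here) because the estimator is a different, shrunken one. At a gain of 1.2 SD it was larger (0.188 against 0.175). The demonstrated problem is bias.
- **That participants unable to finish the 1000 m test are scored as unchanged.** Section 2.5.4 allows walking and does not say how non-completion is recorded. Imputation under missing at random would not settle that case either, since it would generally credit such a person with a completer-like gain.

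**Conclusion.** The concern holds in conditional form. It is certain from the text that the rule is baseline-carried-forward and fixes every missing 12-week change at zero. It follows that the group difference can be shrunk, inflated or created whenever people with missing results did change and the Step 5 balance does not hold. The rule cannot be defended as reliably conservative.

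The size in this trial is unknown. The illustrative range, from a negligible effect at small dropout gaps to a false difference of -0.15 SD with type I error of about 18% at 10% against 40%, rests wholly on the assumed sample size, correlation, gains and outcome-independent dropout. The point still deserves correction because this is the only missing-data method stated, it governs all primary and secondary outcomes, and nothing else in the plan would reveal its influence.

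**What to change.** Replace the imputation sentence in section 2.7 with the following:

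- **Primary analysis:** ANCOVA of the 12-week value on group and baseline, with missing 12-week values handled under missing at random. This can be an observed-data or likelihood-based analysis, or multiple imputation within group using baseline outcome, age and sex. State which one is used.
- **Sensitivity analysis:** keep baseline-carried-forward and call it that. It shows how the conclusion stands if people who stop lose their gain or cannot complete a test, cases in which missing at random is too favourable.
- **Reporting:** the number of missing 12-week results by group and outcome, with reasons.

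The cost is a little more analysis work, possibly outside JASP, and often somewhat wider confidence intervals. Section 2.7 is written in the past tense. If follow-up is over, this means a re-analysis as well as a change of wording, and 12-week results from people who stopped may no longer be obtainable.
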